9.4 DATA SOURCES

The MDV database consists of anonymized administrative claims and DPC data for inpatient and outpatient settings from acute hospitals (mainly considered as advanced treatment hospitals). At present, the database includes >35 million patients from >400 hospitals. Patients in Japan have free access to health care facilities and data from the other hospitals not included in the database are unavailable.

9.5 STUDY SIZE

The planned sample size is not based on the formal statistical hypothesis testing and statistical precision. Because the MDV database consists of >35 million patients, it is expected that the sufficient number of non-IPF fibrosing ILD patients will be included in the study.

9.6 DATA MANAGEMENT

The anonymised data received from hospitals has been checked by data managers in MDV to update the database. The database Boehringer Ingelheim (BI) received from MDV will be used.

The analyses will be performed using Instant Health Data (IHD) platform, SAS statistical software (version 9.3 or higher) and/or R.

9.7 DATA ANALYSIS

9.7.1 Common handling for statistical analysis

Unless otherwise specified, descriptive analysis is planned.

The summary statistics for continuous variables are N, mean, standard deviation, minimum, 25th percentile (Q1), median, 75th percentile (Q3), and maximum.

Tabulations of frequencies for categorical variables will include all possible categories and will display the number of observations in a category as well as percentage (%) relative to the population analysed. The precision for percentage will be one decimal point.

9.7.2 Statistical analysis

9.7.2.1 Patient background characteristics and treatment

- Patient demographics (sex, age at the index date)
- Comorbidity and medical history during 12 months prior to the index date (included)
- Clinical examination, management, and treatment during 6 months prior to the index date (included)
- Duration of follow-up period, which is defined as “end of follow-up period” – “start of follow-up period” + 1 day
- Underlying diseases

These will also be analysed in patients with progression to PF-ILD and those without progression to PF-ILD respectively.

9.7.2.2 Primary outcome

- Incidence probability of progression to PF-ILDs at 6, 12, 18, and 24 months after the index date

Cumulative incidence probability of progression to PF-ILD at 6, 12, 18 and 24 months after the index date will be estimated by using Kaplan-Meier method. Greenwood's variance estimate will be used for calculating 95% confidence interval. Kaplan-Meier curve will also be displayed.

Of the patients with progression to PF-ILD, frequency of patients meeting each criteria of progression to PF-ILD will be analysed descriptively.

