Population:	
Patients who meet all of the inclusion criteria and do not meet any of the exclusion criteria will be included in the study population.
 
Inclusion Criteria:
 
 1) Patients diagnosed with at least two fibrosing ILD codes on different dates in the patient identification period from 01-Jan-2013 to 6 months before 28-May-2020 2) Patients aged 18 years and older on the index date 3) Patients for whom data for the 12 months prior to the index date can be extracted as baseline data 
Exclusion Criteria:
 
 1) Patients grouped into the underlying disease of IPF 2) Patients who have met PF-ILD progression criteria during the baseline period 
Note: only diagnosis records without 'suspect flag' are to be considered for evaluating diagnosis related in/excl criteria"

Variables:	
The following information will be extracted from MDV database in this study; sex, age, comorbidity and medical history of interest, Underlying disease (pre-specified ILD), clinical examination, treatment and management of interest

Data sources:	
The MDV database consists of anonymized administrative claims and Diagnosis Procedure Combination (DPC) data for inpatient and outpatient settings from acute hospitals (mainly considered as advanced treatment hospitals). The database includes >35 million patients from >400 hospitals. Patients in Japan have free access to health care facilities and data from the other hospitals not included in the database are unavailable.

Study size:	
The planned sample size is not based on the formal statistical hypothesis testing and statistical precision. Because the MDV database consists of >35 million patients, it is expected that the sufficient number of non-IPF fibrosing ILD patients will be included in the study.

Data analysis:	
Primary outcome Incidence probability of progression to PF-ILDs at 6, 12, 18, and 24 months after the index date. Cumulative incidence probability will be estimated by using Kaplan-Meier method.
 
Secondary outcomes Management and treatment during follow-up period Frequency of patients with management and treatment of interest during follow-up period will be analyzed descriptively.

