7. RATIONALE AND BACKGROUND

The term interstitial lung disease (ILD) encompasses a large group of over 200 pulmonary disorders. While idiopathic pulmonary fibrosis (IPF) is the best-known progressive fibrosing ILD (PF-ILD), there is a group of patients with different underlying clinical ILD diagnoses other than IPF who develop a progressive fibrosing phenotype during the course of their disease (e.g., idiopathic interstitial pneumonias [IIPs] such as idiopathic nonspecific interstitial pneumonia [iNSIP] and unclassifiable IIP; hypersensitivity pneumonitis [HP]; autoimmune interstitial lung disease [connective tissue disease-ILDs (CTD-ILD) such as rheumatoid arthritis-ILD (RA-ILD), systemic sclerosis-ILD (SSc-ILD) and anti-synthetase syndrome]; Sarcoidosis; Pneumoconiosis/exposure related ILD) [P17-10582, P18-04729, P19-01738, R19-0854]. These patients demonstrate a number of similarities to patients with IPF, with their disease being defined by the presence of progressive pulmonary fibrosis, worsening respiratory symptoms, declining lung function despite immunomodulatory therapies and, ultimately, early mortality.

Although there had been no indicated therapies for patients with chronic fibrosing ILDs with a progressive phenotype (other than IPF), Nintedanib has just been approved for SSc-ILD in the end of Dec. 2019 based on the results of the SENSCIS trial (NCT02597933) [P19-04387] and for PF-ILDs in the end of May 2020 in Japan based on the results of the INBUILD trial (NCT02999178) [P19-08802, P20-02333].

There is minimal literature available to estimate the proportion of patients who develop PF-ILDs in patients with fibrosing ILD other than IPF in Japan. In addition, the current management and treatment for these diseases are not well-known. These information are keys to gaining a better understanding of the size of this population with high unmet need and for physicians, patients and other stakeholders to optimize allocation of resources, diagnostic assessment and management of this patient population.

Therefore, this study will use the database from Medical Data Vision (MDV) to investigate the incidence probability of progression to PF-ILDs according to each co-existing underlying diseases and the characteristics of procedures for management and treatment in patients with fibrosing ILD other than IPF.

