8. RESEARCH QUESTION AND OBJECTIVES

8.1 PRIMARY OBJECTIVE

To investigate the incidence probability of progression to PF-ILDs in patients with fibrosing ILD other than IPF in real-world setting in Japan

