9. RESEARCH METHODS

9.1 STUDY DESIGN

This is a retrospective cohort study using the database from MDV.

Data from 01-Jan-2012 to 28-May-2020 will be used. It will be considered that each patient is observable from his/her first encounter to his/her last encounter in the database. The patients with fibrosing ILD will be identified in the period from 01-Jan-2013 to 6 months before 28-May-2020. Each patient who meets all the inclusion criteria and none of the exclusion criteria will be followed up from the day after the index date* until the end of study period (i.e. 28-May-2020), the last encounter in the MDV database, in-hospital death, whichever occurs first.

*The index date will be the date of the second diagnosis of fibrosing ILD. Please refer to the Section 9.2.2.1 for the detailed codes of fibrosing ILD.

*The index date will depend on the time the patient fulfils the eligibility criteria

Figure 1 . Schematic of the Study Design

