9.3 VARIABLES

9.3.1 Outcomes

9.3.1.1 Primary outcome

Incidence probability of progression to PF-ILDs at 6, 12, 18, and 24 months after the index date*

Progression to PF-ILD as event in this study is defined in Table 1 as well as Annex 2. Event date will be the date when the one of criteria of the progression to PF-ILD is met.

*The index date will be the date of the second diagnosis of fibrosing ILD. Please refer to the Section 9.2.2.1 for the detailed codes of fibrosing ILD.

Table 1. Interstitial lung disease progression proxies

Proxy
- ≥ 3 pulmonary function tests on different dates of service within 365 days - The date of the 3 rd pulmonary function test will be the date of progression
- ≥ 3 HRCT/CT on different dates of service within 365 days - The date of the 3 rd HRCT/CT will be the date of progression
≥ 1 claim for oxygen therapy (HOT) during follow-up period
≥ 1 respiratory hospitalization during follow-up period
≥ 1 claim for palliative care during follow-up period
≥ 1 lung transplant during follow-up period
≥ 1 new* claim for immunosuppressive drugs during follow-up period with at least two out of the three test codes** within 3 months before new claims for immunosuppressive drugs Rituximab Tacrolimus Mycophenolate Cyclosporine Cyclophosphamide Azathioprine Tocilizumab
*: Not received in the 12 months prior to the index date **: ① Pulmonary function tests, ② HRCT/CT, ③ KL-6 or SP-D
≥ 1 new* claim for oral corticosteroid with a prednisone-equivalent dose of >20 mg during follow-up period and with at least two out of the three test codes* within 3 months before new claims for oral corticosteroid *: Not received in the 12 months prior to the index date **: ① Pulmonary function tests, ② HRCT/CT, ③ KL-6 or SP-D
≥ 1 claim for Nintedanib* during follow-up period *: Patients meeting this criterion will be counted only if patients with fibrosing ILDs meet this criterion on or after 29-May-2020, because nintedanib was approved for PF-ILD on 29-May-2020. Even if patients with fibrosing ILDs meet this criterion on or before 28-May-2020, they will not be counted.

HRCT; high-resolution computed tomography, CT; computed tomography, KL-6; krebs von den lungen-6, SP-D; surfactant protein D

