9.7.3 Subgroup analysis

The three subgroup analyses by underlying diseases defined by disease codes on the index date and 12-months lookback period as described in Annex 5 will be performed for patient background characteristics and treatment, primary outcome, and secondary outcomes.

<Subgroup Patterns>

Underlying Autoimmune Disease (Subgroup1): Autoimmune ILD, Non-autoimmune ILD, Multiple, Unknown

ILD Category (Subgroup 2): Hypersensitive pneumonitis, Exposure-related ILD, iNSIP, Unclassifiable IIP, Sarcoidosis, RA-ILD, SSc-ILD, MCTD-ILD, Other autoimmune ILD, Other ILD, Multiple, Unknown

Pre-Specified ILD Clinical Diagnosis (Subgroup 3): Hypersensitive pneumonitis, Exposure-related ILD, iNSIP, Unclassifiable IIP, Sarcoidosis, RA-ILD, SSc-ILD, MCTD-ILD, SLE-ILD, PM/DM-ILD, Sjogren ILD, Other autoimmune ILD, Other ILD, Multiple, Unknown

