ANNEX 2. INTERSTITIAL LUNG DISEASE PROGRESSION PROXIES

Proxy	billing code / generic names / EphMRA ATC code
≥ 3 pulmonary function tests on different dates of service within 365 days The date of the 3 rd pulmonary function test will be the date of progression	160062610 160062710 160062810
≥ 3 HRCT/CT on different dates of service within 365 days The date of the 3 rd HRCT/CT will be the date of progression	170022290 170011710 170011810 170028610 170033410 170034910 170040210 170040410 170040610 170040810 170041010
≥ 1 claim for oxygen therapy (HOT) during follow-up period	114003710
≥ 1 respiratory hospitalization during follow-up period	A221 A379 A370 B250 B440 J00 J01.x J02.x J03.x J04.x J05.x J06.x J110 J12.x J13 J14 J15.x J160 J18.x J20x J21.x J22 J40 J41.x J42 J43.x J44.x J45.x J84.x J96.x Segment of disease based on DPC is “01: Disease name which input the most medical resources”, “11: Main disease name”, or “21: Disease name behind hospitalization”
≥ 1 claim for palliative care during follow-up period	Oxygen inhalation: 140005610 Opioid use:

	N02A0 [Excluding methadone, buprenorphine, naloxonecombinations (Suboxone)] * *transdermal patch, sublingual agent, Transmucosal agent, suppository are excluded
≥ 1 lung transplant during follow-up period	K514-4 K514-6
≥ 1 new* claim for immunosuppressive drugs during follow-up period with at least two out of the three test codes** within 3 months before new claims for immunosuppressive drugs Rituximab Tacrolimus Mycophenolate Cyclosporine Cyclophosphamide Azathioprine Tocilizumab	Rituximab/ L01G1 Tacrolimus/ L04X0 Mycophenolate/ L04X0 Cyclosporine or (Ciclosporin, Cyclosporin) / L04X0 Cyclophosphamide/ L01A0 Azathioprine/ L04X0 Tocilizumab/ M01C0 & L04C0 (Generic names/ MphMRA ATC codes which each drug is under)
≥ 1 new* claim for oral corticosteroid with a prednisone-equivalent dose of >20 mg during follow-up period and with at least two out of the three test codes* within 3 months before new claims for oral corticosteroid *: Not received in the 12 months prior to the index date **: ① Pulmonary function tests, ② HRCT/CT, ③ KL-6 or SP-D	H02A2 excluding Florinef

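### The primary cumulative incidence is Kaplan-Meier with in-hospital death before progression censored, so it can only equal or exceed the true cumulative incidence, by an amount the documents do not allow to be sized

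*Combined protocol and SAP*

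**What the plan says.** The primary objective (section 8.1) is "To investigate the incidence probability of progression to PF-ILDs" in patients with fibrosing ILD other than IPF. The rationale (section 7) gives the gap to be filled as "minimal literature available to estimate the proportion of patients who develop PF-ILDs".

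For the estimator, the abstract states: "Cumulative incidence probability will be estimated by using Kaplan-Meier method". Section 9.7.2.2 repeats this for 6, 12, 18 and "24 months after the index date will be estimated by using Kaplan-Meier method", with Greenwood's variance for the 95% confidence interval.

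Under section 9.1, follow-up runs to the end of the study period, "the last encounter in the MDV database, in-hospital death, whichever occurs first". Section 9.3.1.1 dates the event by the first proxy: "Event date will be the date when the one of criteria of the progression to PF-ILD is met". Death is not among the proxies in Table 1 or Annex 2.

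The same estimator is carried into the three subgroup schemes of section 9.7.3, which cover "primary outcome, and secondary outcomes", and into the repeated analyses of section 9.7.4.

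**The concern.** No censoring rule is written. Read together, though, the follow-up rule, the event definition and the choice of Kaplan-Meier leave only one treatment for an in-hospital death before any proxy: a censored time. Kaplan-Meier assumes that censored patients go on to progress at the same rate as those still under observation. A patient who has died cannot progress, so the result is not the proportion of patients who develop PF-ILD. It is the probability of progression if in-hospital death were removed, and even that needs independent censoring.

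The four headline figures would thus carry a label that does not fit them. Nothing in the plan would reveal the discrepancy. Section 9.7.4 changes the data cut-off, the index date or both, and leaves modified progression criteria optional. Section 9.9 does not mention death. Section 9.7.2.1 tabulates the length of follow-up but not the reason it ended. Subgroup comparisons would be distorted only if deaths before progression differ between subgroups, which is an assumption.

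**Working it through.** The documents give no number of patients, event count, expected incidence or death rate, so there is no figure of the plan's own to reproduce. The check has two parts.

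**1. Direction.** At each event time let R be the number at risk, d₁ the progressions and d₂ the in-hospital deaths before progression.

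- Aalen-Johansen adds S(t−)·d₁/R, where S falls by the factor 1 − (d₁ + d₂)/R.
- One minus Kaplan-Meier adds K(t−)·d₁/R, where K falls by the factor 1 − d₁/R.

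K is never smaller than S, so one minus Kaplan-Meier is never smaller than Aalen-Johansen. In 3000 simulated samples with ties, Weibull hazards and (in half of them) shared frailty, it was never below at any time up to 24 months, apart from rounding at machine precision.

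The gap at time t is above zero only if someone progresses after such a death and by t. A ten-patient example shows this, with progressions at months 3 and 9, one death, and seven patients followed beyond month 24:

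- Death at month 20: both methods give 1/10 + (9/10)(1/9) = 20.0% at 12, 18 and 24 months.
- Death at month 5: both give 10.0% at 6 months. At month 9 eight patients are at risk. Kaplan-Meier gives 1 − (9/10)(7/8) = 21.25%. Aalen-Johansen gives 1/10 + (8/10)(1/8) = 20.0%.

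In a large cohort a positive gap is practically certain overall. In a small subgroup it is not.

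**2. Size, under assumptions not taken from the documents.** Assume constant hazards per year: a for progression and b for in-hospital death before progression. Then:

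- a = −ln(1 − KM₂₄)/2
- KM(t) = 1 − exp(−a·t)
- CIF(t) = a/(a+b) · [1 − exp(−(a+b)·t)]
- D(t) = b/(a+b) · [1 − exp(−(a+b)·t)], the proportion who die in hospital before progression

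For KM₂₄ = 50%, a = 0.6931/2 = 0.3466. At 24 months:

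| b per year | CIF % | Excess (points) | D % |
|---|---|---|---|
| 0.001 | 49.96 | 0.04 | 0.14 |
| 0.002 | 49.91 | 0.09 | 0.29 |
| 0.01 | 49.56 | 0.44 | 1.43 |
| 0.02 | 49.13 | 0.87 | 2.83 |
| 0.05 | 47.85 | 2.15 | 6.90 |
| 0.10 | 45.84 | 4.16 | 13.23 |
| 0.15 | 43.94 | 6.06 | 19.02 |

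At 12 months the excess over the same hazards runs from 0.01 to 2.0 points. With KM₂₄ at 30% the 24-month excess runs from 0.03 to 3.9 points, and at 70% from 0.06 to 7.7 points. At b = 0.15, D is 22% for KM₂₄ = 30% and 15.5% for 70%.

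Solving for b gives the proportion of deaths before any proxy that produces a given 24-month excess, with no other censoring:

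| KM₂₄ | D for a 1-point excess | D for a 0.1-point excess |
|---|---|---|
| 30% | 5.9% | 0.6% |
| 50% | 3.2% | 0.3% |
| 70% | 2.1% | 0.2% |

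The planned report would contain no count to set against this second table.

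**The case against.** The strongest counter-argument is that the event definition absorbs most of the competing event. Only in-hospital deaths are at issue, so the patient is already admitted. Annex 2 counts as progression a respiratory admission, any oxygen-inhalation claim ("Oxygen inhalation: 140005610", with no indication required), most opioid claims and a third CT within 365 days. A death is censored only if it escapes all of these, in the final admission and at every earlier time since index. At hazards of 0.001 to 0.002 per year and Kaplan-Meier 50%, the excess is below the one-decimal precision that section 9.7.1 sets for percentages. This stands as a reason to expect the low end. It does not settle the matter, because the plan never checks it. The respiratory-admission code list contains no lung cancer or coronary disease codes, although both are listed comorbidities in Annex 4. A fatal admission for either would not by itself meet that proxy, though oxygen or an opioid claim still could.

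A second argument is that Kaplan-Meier is openly named and is valid for net risk, that the objective does not say how death is handled, and that the study is descriptive. The first two are true. But the protocol nowhere says that it wants net risk, it labels the result cumulative incidence, and its rationale speaks of a proportion of patients.

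A third is that deaths outside MDV hospitals would still be censored at the last encounter, so Aalen-Johansen is only a partial correction. This stands and should be stated in the protocol. It does not favour censoring the deaths that are recorded.

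Finally, section 9.9 names larger uncertainties: unvalidated definitions, and possible underestimation from care outside the database. These are separate mechanisms and bear on the study's net bias, which is not claimed here.

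**Conclusion.** The concern holds. Following the plan as written gives a figure that is not the cumulative incidence it is called. Relative to the Aalen-Johansen estimate from the same recorded data it can only be equal or too high. Confidence is high for the direction, which is algebraic. The size cannot be derived from the documents. The range of 0.03 to 7.7 points at 24 months rests on assumed constant hazards, death hazards of 0.001 to 0.15 per year and Kaplan-Meier values of 30% to 70%. The low end is the more plausible, and the upper end would need roughly 15% to 22% of patients to die in hospital with no proxy first. None of this says that the study overestimates progression overall. The point should be fixed because it affects the only primary estimator, the plan gives a reader no means of judging the excess, and the remedy is cheap.

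**What to change.** - In section 9.7.2.2 and the abstract, and wherever the primary outcome is repeated (sections 9.7.3 and 9.7.4), estimate cumulative incidence by Aalen-Johansen. Treat in-hospital death before progression as a competing event, and give a matching 95% confidence interval and curve. Keep Kaplan-Meier as a supplementary analysis.
- Write down the censoring rule.
- Report the number and percentage of in-hospital deaths before progression, overall and by subgroup.
- State in section 9.9 that deaths outside MDV hospitals remain censored at the last encounter, so the correction is partial.

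The cost is a wording change and a few lines of SAS or R. No new data are needed, because in-hospital death already ends follow-up. The primary figures will be equal or somewhat lower.

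Version 1.4 is dated 29 Nov. 2023, after the planned final results (Q2 2023) and report (Q3 2023). The documents do not say whether analyses had been run. If they had, Aalen-Johansen should be added alongside the existing figures and labelled as added later.

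### The primary 95% intervals ignore clustering of patients within hospitals and are probably too narrow for the stated target of patients in Japan; the plan does not allow the size to be determined

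*Combined protocol and SAP*

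**What the plan says.** Section 9.7.2.2 fixes the estimator, "Cumulative incidence probability of progression to PF-ILD at 6, 12, 18 and 24 months after the index date will be estimated by using Kaplan-Meier method", and its uncertainty: "Greenwood's variance estimate will be used for calculating 95% confidence interval". No other variance is named for the primary outcome.

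The target in section 8.1 is national: "To investigate the incidence probability of progression to PF-ILDs in patients with fibrosing ILD other than IPF in real-world setting in Japan". On the source, section 9.4 says "At present, the database includes >35 million patients from >400 hospitals". On size, section 9.5 says "The planned sample size is not based on the formal statistical hypothesis testing and statistical precision".

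Table 1 in section 9.3.1.1 defines the event through claims. Among the proxies are "≥ 3 HRCT/CT on different dates of service within 365 days", "≥ 3 pulmonary function tests on different dates of service within 365 days" and "≥ 1 respiratory hospitalization during follow-up period". Others are claims for home oxygen and palliative care (which Annex 2 lets an oxygen-inhalation code satisfy), lung transplant, and new drug claims preceded by two of three test types within 3 months.

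Nothing in the plan provides for correlation within hospitals. The sensitivity analyses in section 9.7.4 change the data cut-off, the index date and possibly the progression criteria. The limitations in section 9.9 cover unvalidated algorithms and care outside the database.

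**The concern.** Greenwood's formula is right when patients' event times are independent. Here two features work against that. Patients are grouped in hospitals, and every proxy in Table 1 records care delivered rather than a measured decline; section 9.9 confirms that lung function results are not in the database. A third CT or a third lung function test within a year counts as progression whatever it shows. A hospital that repeats these tests three times a year as routine will produce events in many of its patients at once. Some correlation within hospitals is therefore very plausible from the endpoint definition alone.

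The study has no hypothesis test and no precision target, so the estimate with its interval is the primary result. Adding patients from the same hospitals, as the first sensitivity analysis in section 9.7.4 may largely do, shrinks Greenwood's interval but not the between-hospital part of the uncertainty.

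**Working it through.** **No figure to reproduce.** The plan states no cohort size, event rate, interval width or intraclass correlation (ICC). From the documents come only the estimator, the Greenwood variance, the 95% level (z = 1.96) and the absence of any cluster term. All inputs below are assumptions: N = 2,000 to 30,000; K = 200 or 400 contributing hospitals; coefficient of variation of hospital size cv = 0 or 1; ICC 0 to 0.10; 12-month incidence p = 40%.

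**Step 1: design effect.** With m = N/K patients per hospital,

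- DE = 1 + [(cv² + 1)·m − 1]·ICC
- Greenwood half-width without censoring = 1.96·√[p(1 − p)/N]
- half-width allowing for clustering = Greenwood half-width × √DE
- actual coverage of the nominal interval = 2Φ(1.96/√DE) − 1

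Worked example: N = 10,000, K = 400, cv = 1, ICC = 0.01. Then m = 25 and DE = 1 + (2 × 25 − 1) × 0.01 = 1.49. Greenwood gives 1.96 × √(0.24/10,000) = 0.96 points. Multiplying by √1.49 = 1.22 gives 1.17 points. Coverage is 2Φ(1.96/1.22) − 1 = 89.2%.

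| N | K | cv | ICC | DE | Half-width, points | Coverage |
|---|---|---|---|---|---|---|
| any | any | any | 0 | 1.00 | unchanged | 95.0% |
| 2,000 | 400 | 0 | 0.01 | 1.04 | 2.15 to 2.19 | 94.5% |
| 2,000 | 200 | 1 | 0.05 | 1.95 | 2.15 to 3.00 | 84.0% |
| 10,000 | 400 | 1 | 0.01 | 1.49 | 0.96 to 1.17 | 89.2% |
| 10,000 | 400 | 1 | 0.05 | 3.45 | 0.96 to 1.78 | 70.9% |
| 30,000 | 400 | 1 | 0.05 | 8.45 | 0.55 to 1.61 | 50.0% |
| 30,000 | 200 | 1 | 0.10 | 30.90 | 0.55 to 3.08 | 27.6% |

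The last row is the widest case examined: 3.08 − 0.55 = 2.53 points.

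**Step 2: why more patients do not help.** The same formula splits the variance into p(1 − p)(1 − ICC)/N + p(1 − p)·ICC·(1 + cv²)/K. The second term does not shrink with N. For K = 400, cv = 1 and ICC = 0.01 it sets a floor of 1.96 × √(0.24 × 0.01 × 2/400) = 0.68 points, while Greenwood's half-width tends to zero.

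**Step 3: simulation with censoring.** Kaplan-Meier with Greenwood intervals; 10,000 patients in 400 hospitals of unequal size (cv about 1); log-normal hospital effect on the hazard; independent censoring; 600 runs per setting. Ratio = empirical SD divided by mean Greenwood standard error.

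| Hospital SD, log hazard | ICC at 12 months | Ratio, 12 months | Coverage, 12 months | Ratio, 24 months | Coverage, 24 months |
|---|---|---|---|---|---|
| 0 | 0 | 0.97 | 96.0% | 1.02 | 94.0% |
| 0.2 | 0.016 | 1.27 | 88.0% | 1.34 | 85.7% |
| 0.4 | 0.06 | 1.88 | 72.3% | 1.90 | 71.5% |
| 0.6 | 0.12 | 2.51 | 56.7% | 2.34 | 59.7% |

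With no hospital variation Greenwood is correct to within simulation error (√(0.95 × 0.05/600) = 0.9 points), so the loss of coverage comes from clustering. Bias in the point estimate is at most 0.1 point throughout. The formula in step 1 agrees with the simulation: at ICC 0.06 it gives √(1 + 49 × 0.06) = 1.98 against a simulated 1.88.

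**The case against.** Greenwood is the standard variance for a Kaplan-Meier estimate, and naming it is not an error in itself. The analysis is descriptive, without a test or decision rule. Coverage looks poor chiefly where the interval is already very tight, and the absolute widening is small. If inference were confined to the participating hospitals, the between-hospital component would largely not apply. Nor would a clustered variance deliver a national estimate: section 9.4 describes acute hospitals, mainly advanced-treatment ones, and a wider interval does not correct for that selection, for unvalidated proxies or for care received elsewhere. Clustered variances are also unreliable with few clusters, and the documents mention no hospital identifier.

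Much of this stands. It limits the size of the point and shapes the remedy, but it does not show that Greenwood alone is adequate for the target in section 8.1.

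Three stronger readings are tempting and not supported:

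- A reader might infer that between-hospital variation dominates the uncertainty. Its share is 1 − 1/DE: about 33% at DE 1.49 and 71% at DE 3.45. Which applies is unknown.
- A reader might infer that subgroups are hit hardest because they sit in a few specialist hospitals. The documents say nothing on where subgroup patients are treated. Rare categories may have few patients per hospital and so a smaller design effect.
- A reader might take the count of over 400 hospitals as the number of clusters. It is the present size of the whole database, not of this cohort.

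**Conclusion.** The point holds as to direction. The plan's only interval for the primary outcome assumes independent patients. The endpoint makes correlation within hospitals very plausible, and the target extends beyond these hospitals. The intervals are therefore likely too narrow.

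A reader might go further and call them definitely or severely too narrow. The documents do not support that, because the result rests on an ICC, a cohort size and a number of contributing hospitals that they do not give. Across the assumed inputs the effect runs from none (ICC 0) or almost none (coverage 94.5%) to coverage of about 70% or lower, with half-widths larger by roughly 0 to 2.5 percentage points. Nor is the event purely local practice: home oxygen and transplant also reflect severity. The point estimates are not in question here. Because the interval is part of the primary result and the remedy is cheap, the change should be made.

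**What to change.** In section 9.7.2.2, compute the Kaplan-Meier 95% intervals with a variance clustered on hospital (robust or infinitesimal jackknife) or with a bootstrap that resamples whole hospitals. Report Greenwood's interval alongside. Report also the number of contributing hospitals and the spread of hospital-level incidence, which would show readers how far local practice drives the event.

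For the subgroups in section 9.7.3, use the clustered interval only where enough hospitals contribute, and flag the remaining categories.

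This assumes that the sponsor's copy of the data carries a masked hospital identifier. If it does not, section 9.9 should state that the intervals ignore hospital clustering and probably understate uncertainty. In either case, section 9.9 should say that clustered intervals do not correct for the selection of acute hospitals.

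The cost is a few sentences, a little more analysis with standard software, and wider reported intervals. No new data are needed if the identifier exists, and the point estimates do not change.
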